9.2.2 Monitoring Participants Pregnancies for Potential SAEs

Known pregnancy at the time of enrolment is an exclusion criterion for the **RePHILL** trial, however, should a participant later be found to have been pregnant at the time of trauma and received the trial intervention, the outcome of the pregnancy (spontaneous miscarriage, elective termination, normal birth or congenital abnormality) must be followed-up and documented, even if the participant withdrew consent from follow-up within the trial. Initial notification of pregnancy will be done via a SAE form and the outcome of the pregnancy will be recorded on the Pregnancy Notification Form. These will be reported to the **RePHILL** Trial Office.

9.2.3 Reporting Period

Details of all SAEs (except those listed as excluded) will be documented and reported from the date of commencement of protocol defined treatment.

9.3 Reporting Procedure – Site

9.3.1 Serious Adverse Events

Receiving hospitals should report SAE's which are NOT listed as recognised complications of major trauma (as defined in section 9.2.1), to the **RePHILL** Trial Office on a SAE Form as soon as possible and no later than 24 hours after becoming aware of the event.

Complete SAE Forms should be faxed to the **RePHILL** Trial Office on:

[name] or [name]

The research team at site will be required to respond to any related queries raised by the **RePHILL** Trial Office as soon as possible.

Site Investigators should also notify their own institutions of any SAEs in accordance with their institutional policies.

For SAE Forms completed by someone other than the Investigator, the Investigator will be required to countersign the original SAE Form to confirm agreement with the categorisation of seriousness and causality assessments. The SAE Form should then be returned to the **RePHILL** Trial Office and a copy retained at site.

9.3.2 Provision of Follow-up Information

Participants should be followed up until resolution or stabilisation of the event. Follow-up information should be provided as soon as available.

9.4 Reporting Procedure – Trial Office

On receipt of the SAE form, the **RePHILL** Trial Office will allocate each SAE a unique reference number which will be forwarded to the receiving hospital as proof of receipt. The SAE reference number should be quoted on all correspondence and follow-up reports regarding the SAE.

On receipt of an SAE Form, seriousness and causality will be reviewed independently by the Chief Investigator (CI; or nominated delegate). A SAE judged to have a reasonable causal relationship with the trial intervention will be regarded as a Serious Adverse Reaction (SAR). The causality assessment given by the PI will not be downgraded by the CI *"or delegate(s)"*. If the CI *"or delegate(s)"* disagrees with the PI's causality assessment, the opinion of both parties will be documented, and where the event requires further reporting, the opinion will be provided with the report.

The CI (or nominated individual will also assess all SARs for expectedness. If the event meets the definition of a SAR that is unexpected (i.e. is not defined in the approved version of the Reference Safety Information) it will be classified as a Suspected Unexpected Serious Adverse Reaction (SUSAR).

9.5 Reporting to the Competent Authority and Research Ethics Committee

9.5.1 Suspected Unexpected Serious Adverse Reactions

The **RePHILL** Trial Office will report a minimal data set of all individual events categorised as a fatal or life threatening SUSAR to the Medicines and Healthcare products Regulatory Agency (MHRA) and REC within 7 days. Detailed follow-up information will be provided within an additional 8 days.

All other events categorised as non-life threatening SUSARs will be reported within 15 days.

A copy will be sent to the Trial Sponsor at the time of sending the SUSAR report.

9.5.2 Serious Adverse Reactions

The **RePHILL** Trial Office will report details of all SAEs and SARs (including SUSARs) to the MHRA and REC annually from the date of the Clinical Trial Authorisation, in the form of a Development Safety Update Report (DSUR).

A copy will also be sent to the Sponsor at the time of sending out the DSUR.

9.5.3 Other Safety Issues Identified during the Course of the Trial

The MHRA, REC and Sponsor will be notified immediately if a significant safety issue is identified during the course of the trial.

9.6 Investigators

Details of all SUSARs and any other safety issue(s) which arise during the course of the trial will be reported to Principal Investigators (PI). A copy of any such correspondence should be filed in the Investigator Site File (ISF).

9.7 Haemovigilance

Staff at IDS will be responsible for reporting all transfusion-related adverse events via Serious Hazards Of Transfusion and Serious Adverse Blood Reactions and Events (SHOT/SABRE) according to standard procedures, as required under the regulations of the EU Blood Safety Directive[35, 36]. Similarly, the receiving hospital staff are also responsible for reporting all transfusion-related adverse events, including acute transfusion reactions (<24 hr) and delayed transfusion reactions (>24 hr), to SHOT/SABRE according to standard procedures.

Each individual blood bank issuing blood will have their own their local policies and procedures for the response to a possible transfusion event and should ensure full compliance with their own licence and MHRA. Where the receiving hospital blood bank is different from the issuing hospital blood bank, then both parties should co-ordinate to ensure traceability and reporting.

The hospital blood transfusion laboratory that provided the PRBC (coordinating blood bank) must be informed immediately of all adverse events and reactions. Advice on clinical management and investigation of serious adverse reactions can be obtained from the hospital consultant responsible for blood transfusion at the coordinating blood bank.

9.8 Developmental Safety Update Reports

The **RePHILL** Trial Office will provide the MHRA with DSURs. The reports will be submitted within 60 days of the Development International Birth Date (DIBD) of the trial each year until the trial is declared ended.

9.9 Annual Progress Reports

An Annual Progress Report will be submitted to the REC within 30 days of the anniversary date on which the favourable opinion was given and annually until the trial is declared ended. A copy will also be sent to the Sponsor at the time of sending out the DSUR.

9.10 Reporting Urgent Safety Measures

If any urgent safety measures are taken, the CI/BCTU shall immediately, and in any event no later than 3 days from the date the measures are taken, give written notice to the REC and MHRA of the measures taken and the circumstances giving rise to those measures.

9.11 Notification of Serious Breaches of Good Clinical Practice and/or the Protocol

In accordance with Regulation 29A of the Medicines for Human Use (Clinical Trials) Regulations 2004 and its amendments, the Sponsor of the trial is responsible for notifying the licensing authority in writing of any serious breach of the conditions and principles of Good Clinical Practice (GCP) in connection with that trial or the protocol relating to that trial, within 7 days of becoming aware of that breach.

For the purposes of this regulation, a "serious breach" is a breach which is likely to effect to a significant degree the safety or physical or mental integrity of the subjects of the trial; or the scientific value of the trial. Sites are therefore requested to notify the **RePHILL** Trial office of any suspected trial-related serious breach of GCP and/or the trial protocol. Where the **RePHILL** Trial office is investigating whether or not a serious breach has occurred, sites are also requested to cooperate with the Trial Office in providing sufficient information to report the breach to the MHRA where required and in undertaking any corrective and/or preventive action. Sites may be suspended from further recruitment in the event of serious and persistent non-compliance with the protocol and/or GCP, and/or poor recruitment.

The BCTU on behalf of the Sponsor shall notify the MHRA and REC in writing of serious breaches.

10. Data Management and Quality Assurance

10.1 Confidentiality

All data will be handled in accordance with the UK Data Protection Act 1998.

10.2 Data Collection

During the hospital admission, up to withdrawal, discharge from acute care, death or day 30 (whichever is earlier), where possible, outcome data will be extracted from participant's clinical notes and laboratory reports, to complete the **RePHILL** trial CRFs (**Table 5**).

Table 5: RePHILL Trial CRFs

Form Name	Schedule for Submission
PHEM CRF	As soon as possible following admission
ED Admission CRF	As soon as possible following admission
Confirmation of Consent Form	As soon as possible following admission
2, 6, 12 and 24 hour Follow-Up CRFs	As soon as possible after each time point
ROTEM CRF	As soon as possible after each time point
Impedance Aggregometry and NIRS CRF	As soon as possible after each time point
Daily Assessments	As soon as possible
Medical History CRF	When a full medical history for the participant is available
Exit Form	Where applicable, as soon as possible after exit event
Serious Adverse Event Form	Faxed within 24 hours of research site becoming aware of event
Pregnancy Notification Form	When outcome information on the pregnancy is available

It is the responsibility of the Investigator to ensure the accuracy of all data entered in the CRFs. The **RePHILL** Trial Signature and Delegation Log will identify all those personnel with responsibilities for data collection. The Trial Office must be informed immediately of any change in the site research team.

Prior to commencing recruitment all sites will undergo a process of initiation and will have completed GCP training. Key members of the site research team will be required to attend either a meeting or a teleconference covering aspects of the trial design, protocol procedures, AE, collection and reporting of data and record keeping. Sites will be provided with an ISF containing essential documentation, instructions, and other documentation required for the conduct of the trial.

The CRFs will comprise, but will not necessarily be limited to those listed in Table 5.

If paper CRFs are being completed, they must be signed and dated and returned to the **RePHILL** Trial Office by the PI or an authorised member of the site research team (as delegated on the **RePHILL** Trial Signature & Delegation Log) within the timeframe listed in the table above. Entries on paper CRFs should be made in ballpoint pen, in black ink, and must be legible. Any errors should be crossed out with a single stroke, the correction inserted and the change initialled and dated. If it is not obvious why a change has been made, an explanation should be written next to the change. Data reported on each CRF should be consistent with the related source data or the discrepancies should be explained. If information is not known, this must be clearly indicated on the CRF. All sections should be completed; all missing and ambiguous data will be queried. In all cases it remains the responsibility of the PI to ensure that the CRF has been completed correctly and that the data are accurate. Paper CRFs received will be entered onto the trial database by a trained member of the BCTU trial team.

If remote electronic data entry is being undertaken then CRFs should be entered online at: https://www.trials.bham.ac.uk/RePHILL. Authorised staff at IDS and RHS will require an individual secure login username and password to access this online data entry system. As above, data reported should be consistent with the related source data and all missing and erroneous data will be queried.

CRF version numbers may be updated by the **RePHILL** Trial Office, as appropriate, throughout the duration of the trial. Whilst this will not constitute a protocol amendment, new versions of the CRFs must be implemented by participating sites immediately on receipt.

It will be the responsibility of the PI to ensure the accuracy of all data entered in the CRFs. The RePHILL Trial Signature and Delegation Log will identify all those personnel with responsibilities for data collection.

Access to data, including the final trial dataset will be limited to the Research Team.

The investigator(s)/ institution(s) will permit trial-related monitoring, audits REC review and regulatory inspection(s), providing direct access to source data/ documents. Trial participants are informed of this during the informed consent discussion and will consent to provide access their medical notes.

11. Statistical Considerations

11.1 Sample Size

Although no definitive data exists on this composite outcome, the observational studies suggest potentially dramatic reductions in mortality from civilian pre-hospital PRBC[21] and military pre-hospital PRBC with thawed plasma[17]. Following extensive consultation with experts in pre-hospital trauma resuscitation, it is considered that an absolute reduction of 10% in the proportion of patients experiencing one of the component primary outcomes is clinically meaningful for the patients and is an appropriate effect size upon which to base the power calculation.

To detect an absolute difference of 10% between groups in the proportion of patients experiencing either episode mortality or lactate clearance <20%/h in the two hours post-randomisation (i.e. from 20% in the standard care group to 10% in the group receiving PHBP) using the method of difference between proportions (2-sided Fisher's Exact Test) with 80% power, and a type 1 error rate of 5% (i.e. α =0.05), requires 219 participants per group to be randomised, 438 participants in total. Assuming and adjusting for a 10% loss to follow-up rate, 490 participants will need to be recruited.

11.2 Analysis of Outcome Measures

A separate Statistical Analysis Plan (SAP) will be produced and will provide a more comprehensive description of the planned statistical analyses. A brief outline of these analyses is given below.

The primary comparison groups will be composed of those resuscitated with PHBP versus those resuscitated with normal saline. All analyses will be based on the intention to treat principle, i.e. all participants will be analysed in the groups to which they were allocated irrespective of compliance with the randomised treatment allocation or other protocol violation. For all major outcome measures, summary statistics and differences between groups (e.g. mean differences, relative risks, hazard ratios) will be presented, with 95% confidence intervals and p-values from two-sided tests also given. The data will be assessed for normality and appropriate data transformations or non-parametric tests will be used if necessary. Outcomes will be adjusted for the minimisation variable, IDS, where possible. A p-value of <0.05 will be considered statistically significant, and no adjustment for multiple comparisons will be made.

11.2.1 Primary Outcome Analysis

The primary outcome is a composite measure of episode mortalityvii and early lactate clearance (see section 7.2.4 for formula for calculating lactate clearance) and is measured as a binary outcome. Participants clearing less than 20% per hour of their lactate between randomisation and 2 hours after randomisation or dying will be defined as experiencing the primary outcome. A log-binomial regression model, adjusting for IDS, will be used to calculate the relative risk and 95% confidence interval. As this is a composite endpoint, it will also be reported in accordance with the recommendations of Ferreira-González et al[37].

11.2.2 Secondary Outcome Analysis

Dichotomous data (e.g. development of ARDS, mortality at specified time-points) will be analysed in the same way as the primary outcome. Survival data (e.g. mortality) will be analysed using the log-rank test with a Cox Proportional Hazard model used to calculate hazard ratios, if the assumptions of proportionality are met. Continuous outcomes (e.g. pre-hospital fluid volume, vital signs) will be analysed at specified time-points using linear regression models, with mean differences and 95% confidence intervals reported.

VII Episode mortality refers to mortality between time of injury/ recruitment and discharge from the primary receiving facility to non-acute care, i.e. discharge home or to long-term care, to rehabilitation or repatriation to a hospital closer to their normal residence.

11.2.3 Subgroup Analyses

Eleven a priori subgroup analyses are planned with respect to both the primary and secondary outcome measures. The subgroups will be IDS, mode of transport (air .vs. ground), initial lactate concentration ($\leq 2.2 \text{ mmol/L}$.vs. >2.2 mmol/L), time to ED from injury ($\leq 1 \text{ hour .vs. >1 hour}$), mode of injury (blunt, penetrating, crush), volume of pre-hospital fluid given (total intervention 4 units) vs. those not receiving the total intervention), age (<50 years, 50-70 years, >70 years), head injury (positive vs. negative), compressible haemorrhage (compressible haemorrhage vs. non-compressible haemorrhage), pre-morbid drug history (anticoagulant or antiplatelet medication vs. no anticoagulant or antiplatelet medication) and age of blood products (<8 days vs. ≥ 8 days). Tests for statistical heterogeneity (e.g. by including the treatment group by subgroup interaction parameter in the regression model) will be performed prior to any examination of effect estimates within subgroups. The results of subgroups will be treated with caution and will be used for the purposes of hypothesis generation only.

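### Effect modification by age and initial lactate is tested only in bands, which discards information in interaction tests that already have little power

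*Protocol*

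**What the plan says.** Section 11.2.3 plans the subgroup work in these terms: "Eleven a priori subgroup analyses are planned with respect to both the primary and secondary outcome measures". Age appears as "age (<50 years, 50-70 years, >70 years"), that is, three bands. The factor "initial lactate concentration" is split into two groups at 2.2 mmol/L.

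The same section contains two safeguards. Heterogeneity tests, for example a treatment-by-subgroup interaction term in the regression model, "will be performed prior to any examination of effect estimates within subgroups". The section also says: "The results of subgroups will be treated with caution and will be used for the purposes of hypothesis generation only".

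Section 11.2 sets the threshold for the whole analysis: "A p-value of <0.05 will be considered statistically significant, and no adjustment for multiple comparisons will be made". Section 11.2.2 adds that continuous outcomes "will be analysed at specified time-points using linear regression models". The sample size in section 11.1 rests on the overall comparison of 20% with 10%. The protocol gives no power for any interaction.

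**The concern.** Initial lactate is measured as a concentration before the intervention (section 7.1), and age is a number. Once each is cut into bands, everyone within a band is treated alike. A participant with a lactate just above 2.2 mmol/L is then grouped with one whose lactate is several times higher. If the benefit of blood products changes gradually with age or with depth of shock, the banded test sees only part of that gradient.

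Interaction tests in a trial sized for its main effect have little power to begin with. Banding lowers it further and saves nothing, since the numeric values are already collected. A real gradient could be reported as no evidence of heterogeneity, which makes the list a weaker source of hypotheses, its only stated purpose.

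**Working it through.** **1. The plan's own figure.** Section 11.1 gives 219 per group for 20% against 10%, two-sided 5%, 80% power, Fisher's exact test. The two-proportion formula with continuity correction gives 219. Exact Fisher power at 219 per group is 81.2%. With 10% loss, 438/0.9 = 487, close to the stated 490. The size is sound for the overall effect.

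**2. Power for an interaction on the primary outcome.** Assumptions: two strata, control risk 20% in both, average effect 10 points, effects differing by 10 points with the larger effect in the smaller stratum, and a normal approximation on the risk difference. The stratum shares are assumed. Power = Φ(0.10/SE − 1.96).

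At 438 participants split 50:50 there are 109.5 per arm per stratum, with treated risks of 5% and 15%:

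SE² = (0.16 + 0.0475)/109.5 + (0.16 + 0.1275)/109.5 = 0.00452, so SE = 0.0672, 0.10/SE = 1.49, power = 32%.

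| Split | N = 438 | N = 490 |
|---|---|---|
| 50:50 | 32% | 35% |
| 20:80 | 27% | 29% |
| 10:90 | 18% | 20% |

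Two qualifications apply.
- A 20-point interaction in equal strata (20 points in one, none in the other) has 86% to 89% power, so very large modification would be seen.
- The planned model works on relative risks, and power depends on the scale. For the 50:50 case at 438, the relative risks are 0.25 and 0.75. The variance of the difference in log relative risk is (4 + 19 + 4 + 5.67)/109.5 = 0.298, so SE = 0.546, ln 3/0.546 = 2.01, and power is about 52%. This rests on only about 109.5 × 0.05 = 5.5 expected events in the smallest cell, and is still well short of 80%.

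**3. Information kept by a two-way cut (lactate).** For a normal modifier acting linearly, a cut leaving a share p below it keeps φ(z_p)²/[p(1 − p)].
- 50:50: 0.3989²/0.25 = 64%
- 20:80: 0.2800²/0.16 = 49%
- 10:90: 0.1755²/0.09 = 34%

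For this one test, that is like analysing about 279, 215 or 150 of 438 participants (438 × 0.637, 0.490, 0.342).

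**4. Information kept by three bands (age).** The share kept is the sum over bands of [φ(lower cut) − φ(upper cut)]² / band share, without counting the extra degree of freedom.
- Equal thirds: 2 × 0.3636²/0.3333 = 79%
- 50:30:20: 0.3989²/0.5 + (0.3989 − 0.2800)²/0.3 + 0.2800²/0.2 = 76%
- 60:25:15: 71%
- 70:20:10: 63%

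The two-way figures in step 3 should therefore not be applied to age.

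**5. Number of tests, for context only.** Section 3.3.2 has 13 secondary bullets. With the primary, 14 × 11 = 154 tests, and 154 × 0.05 = 7.7 significant by chance if nothing modifies the effect.

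Counting each post-baseline time-point gives 1 primary + 2 components + 2 mortality + 3 pre-hospital + 15 vital signs + 2 lactate + 3 coagulopathy + 1 ROTEM + 1 platelet function + 3 blood products + 1 ARDS + 1 transfusion complications + 1 organ failure-free days = 36. Then 36 × 11 = 396 tests, 19.8 by chance. Adding the scene vital signs (3) and splitting the ROTEM and MultiPlate assays (3 more) gives 42 × 11 = 462, 23.1 by chance. These expectations do not depend on the tests being independent.

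**The case against.** Section 11.2.3 already does much of what good practice asks. The factors are named in advance, an interaction test precedes any within-subgroup estimate, the results are labelled exploratory, and the section ties no trial decision to them. The interaction term is offered as an example, so a continuous term is not clearly barred. Bands are easier to read, and if the effect truly changed at a threshold such as 2.2 mmol/L, the banded test would be the better one. Section 5.4 also allows only a partial date of birth, if available, for participants who die before hospital, so age may be imprecise for some.

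Most of this stands and keeps the point small. It does not remove it: the section defines these two factors only by their bands, no reason is given to expect a step at those cut-points, and imprecise age affects banded and continuous analyses alike.

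A reader might go further and infer that the plan commits to about 400 interaction tests and 20 false findings, and is therefore unsound, particularly as "no adjustment for multiple comparisons will be made". The protocol does not support that. It does not say that every secondary outcome is tested at every time-point; the count runs from 154 to 462 by counting rule. One factor, age of blood products, has no counterpart in the saline arm and may not yield an estimable interaction. A reader might also infer that the low-lactate band will be small, or that age and lactate are the likeliest modifiers. The protocol gives no lactate distribution and no such ranking.

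**Conclusion.** The point holds as a minor improvement. Age and initial lactate are tested in bands although numeric values are available. The loss is about 36% to 66% of the information for lactate at splits from 50:50 to 10:90, and about 21% to 37% for age in three bands. This assumes roughly normal modifiers, linear modification and the band shares shown. Power for a 10-point interaction in a two-stratum factor is already only about 18% to 35% on the risk-difference scale (about 52% at best among the cases worked here when the 50:50 case at 438 is taken on the log relative-risk scale), so the loss falls where it can least be afforded.

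Nothing here touches the primary analysis, the sample size or the stopping guidance. The number of tests is context for reading the results. Given the exploratory label, it is not a separate fault.

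**What to change.** In the SAP, test the treatment interaction for age and for initial lactate with the factor as a continuous term: age in years and log lactate, each with a pre-specified spline if linearity is doubtful. Keep the protocol's bands to display estimates and confidence intervals. No new data are needed. The cost is a few lines of SAP text and a commitment to a functional form before the data are seen; a badly chosen form would lose some of the gain.

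State in the report how many interaction tests were carried out, so that readers can set nominally significant results against the number expected by chance. Restricting subgroup analyses to the primary outcome and its two components (3 × 11 = 33 tests, about 1.7 expected by chance) is an option. It gives up exploratory results on the other secondary outcomes, and the protocol's hypothesis-generating label makes it a matter of preference.

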3.1.2 Secondary Objectives

To test the hypotheses that, when compared to standard care, does PHBP resuscitation:

- I. Improve blood pressure, heart rate and capillary oxygenation on ED arrival?
- II. Prolong on-scene time?
- III. Reduce pre-hospital fluid requirements?
- IV. Reduce in-hospital transfusion requirements?
- V. Reduce trauma-induced coagulopathy?
- VI. Preserve platelet function?
- VII. Lead to a greater incidence of transfusion-related complications, particularly acute respiratory distress syndrome?
- VIII. Lead to blood product wastage?

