7.1.1 Subsequent Boluses

In both arms of the trial: if a SBP of \geq 90 mmHg or a radial pulse returns after the administration of a bolus and remains present, no further fluid will be administered. If a SBP of \geq 90 mmHg or the radial pulse does not return or if it is subsequently lost, further boluses will be administered until it is restored. In each case a maximum of 4 boluses can be administered as part of the trial interventions.

Any additional fluid boluses required to maintain blood pressure after administration of the 4 trial boluses should be given according to standard local practice.

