8.1.2 Crystalloid Arm

The crystalloid resuscitation comparator arm will consist of 0.9% sodium chloride (normal saline; a solution of sodium chloride in water). This is classified as the comparator IMP in the **RePHILL** trial.

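### Three of the eleven planned subgroups are not baseline factors: receipt of all four units depends on response to treatment, age of the trial blood products has no value in the saline arm, and time to ED is partly post-randomisation

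*Protocol*

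**What the plan says.** Section 11.2.3 lists eleven subgroups for the primary and the secondary outcomes. Three matter here:

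- fluid volume: "volume of pre-hospital fluid given (total intervention 4 units) vs. those not receiving the total intervention";
- product age, cut at 8 days: "no anticoagulant or antiplatelet medication) and age of blood products";
- time from injury to ED, cut at 1 hour.

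Heterogeneity is to be tested, for example "by including the treatment group by subgroup interaction parameter in the regression model", before effects within subgroups are examined. The results are described as exploratory.

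Other sections bear on these three factors:

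- Section 6.2: a participant is randomised when the first transport box is opened.
- Section 7.1.1: once pressure or pulse "returns after the administration of a bolus and remains present, no further fluid will be administered".
- Section 8.1.2: "The crystalloid resuscitation comparator arm will consist of 0.9% sodium chloride".
- Section 3.1.2: lower pre-hospital fluid requirement is a hypothesised effect, and so is "Prolong on-scene time".
- Section 3.3.2: pre-hospital time and fluid volume are secondary outcomes.
- Section 5.4: some randomised participants may die at scene.

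**The concern.** A subgroup comparison keeps the protection of randomisation only if the stratum is fixed before treatment can act on it. If the allocated fluid changes who ends up in a stratum, the two arms within that stratum hold different kinds of patient. A difference in outcome can then appear with no treatment effect at all. A factor that exists in only one arm cannot modify a between-arm effect in any estimable sense.

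The stake is the credibility of these exploratory results. A reader of the final report could take apparent harm or benefit among participants who received all four units as a dose finding when it reflects selection. Because the subgroups also apply to the secondary outcomes, the plan as written would analyse fluid volume within strata defined by fluid volume.

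**Working it through.** **The plan's own figure.** Section 11.2.3 gives no number. For context, the sample size in section 11.1 ("from 20% in the standard care group to 10% in the group receiving PHBP", "2-sided Fisher's Exact Test", 80% power, 5% type 1 error) reproduces: 199 per group by the normal approximation, 219 with continuity correction, and exact Fisher power of 81.2% at 219. Allowing for 10% loss, 438/0.9 = 487, against the stated 490. Nothing below alters it.

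**1. Four units versus fewer.** Box opening comes first, then boluses, then the response that decides whether boluses continue. The stratum is therefore set after randomisation and partly by the allocated fluid.

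To show what this can do, let S be a standard normal severity that drives both the need for four units (M) and the outcome (Y), with no treatment effect on Y. All inputs are assumptions, because the protocol gives no bolus distribution:

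- logit P(M=1) = 0.2 + 1.2·S + d·PHBP
- logit P(Y=1) = −1.4 + 1.2·S
- stratum risk in an arm = E[P(Y|S)·P(M|S, arm)] / E[P(M|S, arm)], and likewise with 1 − P(M) for fewer than four units.

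In the saline arm 53.9% receive all four; the risks are 0.3270 (four) and 0.1587 (fewer).

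| PHBP receiving four | Risk, four | Risk, fewer | RR, four | RR, fewer | Ratio of RRs |
|---|---|---|---|---|---|
| 53.9% (d = 0) | 0.3270 | 0.1587 | 1.00 | 1.00 | 1.00 |
| 49.9% (4 points fewer) | 0.3349 | 0.1642 | 1.02 | 1.03 | 0.99 |
| 38.5% (d = −0.8) | 0.3595 | 0.1803 | 1.10 | 1.14 | 0.97 |
| 68.6% (d = +0.8) | 0.2999 | 0.1389 | 0.92 | 0.88 | 1.05 |

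For example, 0.3595/0.3270 = 1.10 and 0.1803/0.1587 = 1.14. The true overall RR is 1.00 in every row. Both strata move the same way, so their ratio stays close to 1.

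At 245 per arm with d = −0.8, nominal 5% tests reject about 8% of the time (four units), 6% (fewer) and 5% (interaction).

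A second set of assumptions uses a severity slope of 1.5, 20% overall risk and 60% of saline participants receiving four:

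| PHBP receiving four | RR, four | RR, fewer |
|---|---|---|
| 60% | 1.00 | 1.00 |
| 50% | 1.09 | 1.14 |
| 40% | 1.18 | 1.30 |
| 30% | 1.30 | 1.47 |

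At 30% the rejection rates are 25%, 18% and 6% respectively.

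**2. Age of blood products.** Read as the trial products, the factor has values only in the PHBP arm. Coding saline participants as zero makes the interaction column identical to the subgroup column. The design matrix (intercept, arm, age, arm × age) then has rank 3 of 4, and the interaction is not estimable.

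Read as products given in hospital, saline participants can have a value, but only if they are transfused, and that happens after randomisation.

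**3. Time from injury to ED.** Time to ED = (injury to box opening) + (box opening to ED). The first part precedes treatment. The second part includes on-scene time, which the protocol hypothesises PHBP may prolong. A participant who dies at scene has no ED arrival, yet has had a primary-outcome event, so that event falls outside both strata. The documents give no figure from which to size any bias.

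**The case against.** **Ordering and status.** The protocol tests heterogeneity before looking within strata and treats the results as exploratory. In the model above that test is significant about 5% of the time, so the biased estimates would seldom be examined if the ordering is kept. This limits the consequence. It does not make the strata valid, and because both strata shift together, a non-significant heterogeneity test gives no reassurance about them.

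**Biased interaction tests.** A reader might infer that the interaction tests themselves are seriously biased. The numbers do not support that for fluid volume: the distortion is in the within-stratum estimates, and the interaction test stays near its nominal level.

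**Assumed magnitude.** No simulation input comes from the protocol, and with equal need for four units there is no bias. This stands: the sizes are illustrations. Section 7.1 does say that volumes are similar across arms over four boluses (2 × 270 + 2 × 213 = 966 mL against 4 × 250 = 1,000 mL), but that does not say how often four are needed.

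**Product age.** Section 11.2.3 does not say which products are meant, and section 2.4 expects equivalent products to be given in hospital. It is therefore not established that saline participants have no data on any reading. The interaction model is also only an example, so a within-arm analysis is not excluded. Either reading still leaves a factor that is not a baseline one.

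**Time to ED.** A reader might put this on a par with fluid volume. The documents do not support that, since part of the interval precedes randomisation and nothing shows that treatment moves patients across the 1-hour cut.

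**Deferral to the SAP.** Fuller detail is deferred there, but the protocol itself fixes the list of eleven and does not separate these three from the baseline factors.

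**Conclusion.** The point holds for three of the eleven subgroups, with different force.

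- **Fluid volume** is the clearest case. Its strata are formed by response to the allocated fluid, so within-stratum effects are open to selection bias in either direction. Under the first set of assumptions the null RRs run from 1.00 (no difference in need) to 1.10 and 1.14 (15 points fewer) or 0.92 and 0.88 (15 points more). They are larger under the stronger assumptions of the second set. This rests on severity driving both bolus need and outcome, and on the arms differing in bolus need, which the protocol hypothesises but does not quantify.
- **Product age** has a non-estimable interaction if trial products are meant, and is post-randomisation and conditional on transfusion otherwise.
- **Time to ED** is a mixed variable, undefined for deaths at scene, with bias of unknown size.

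The documents give no ground for extending this to the primary analysis, the sample size or the trial's main conclusion.

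**What to change.** In section 11.2.3, and in the SAP to match:

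1. Remove fluid volume as a subgroup and keep it as the secondary outcome it already is.
2. State which products product age refers to, and describe it within the PHBP arm only, with no interaction test.
3. Replace time from injury to ED with time from injury to box opening, or keep it under an explicit label as a non-randomised exploratory analysis that says how deaths at scene are handled.
4. For the remaining factors, use the value known at or before box opening where there is one, and label any others as non-randomised. Mode of transport needs checking, since the protocol does not say when it is fixed.

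The cost is wording. The existing plan already needs the injury time (for time to ED) and the box-opening time (for the 2-hour lactate), so no new data are required. The loss is two exploratory between-arm comparisons: fluid volume and product age.
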